## **15 CMS JUSTIFICATION**

All people who are diagnosed with end stage renal disease (ESRD) in the United States are eligible to enroll in Medicare, regardless of age, subject to the accumulation of sufficient lifetime working credits. In the current population of patients undergoing maintenance dialysis for the treatment of ESRD, approximately 80% are enrolled in either traditional Medicare (as the primary payer of medical care) or Medicare Advantage. A substantial portion of the remainder of patients have private insurance; among these patients, Medicare is the secondary payer of health care services during the first 36 months of maintenance dialysis.

Because study participants will be enrolled from the prevalent dialysis patient population, it is expected that the vast majority of patients that are enrolled in this study will already carry Medicare coverage. Therefore, the results of this study are expected to be highly generalizable to the Medicare population.

## **16 EXTENDED TREATMENT PHASE**

Patients who complete the HOME RUN Trial protocol will be permitted via new informed consent to remain on the SC+ in the home setting for a period not exceeding 30 months or until FDA clearance is granted for home use. The SC+ would be in use under the prescription of their treating nephrologist (i.e., site investigator) with a care partner. Following study completion, the subjects may remain enrolled in the study and undergo safety reporting as defined in [Section 9 Safety](#). However, the subject will no longer have study visits scheduled to collect data relevant to the endpoints and scientific soundness of the study. Subjects will be instructed to report any device-related medical events or deficiencies throughout the extended treatment phase. As defined in [Section 14.7](#), the SCEC will review all SAEs reported in this study phase and the human factors engineer will participate when a device related event is identified.

During the extended treatment phase, the assessments shown in the table below will be performed. The analysis of the primary and secondary endpoints will exclude the data collected from this extended treatment phase. At the conclusion of the extended treatment phase, all data collected during extended treatment will be summarized.

Month(s)	Follow-up Phase	1	2	3	4	5	6	7	8	9	10	11	12	13	14	15	16	17	18	Withdrawal
Informed consent,	x																			NA
Vital signs – Weekly		x	x	x	x	x	x	x	x	x	x	x	x	x	x	x	x	x	x	
RO water/dialysate quality  - Monthly		x	x	x	x	x	x	x	x	x	x	x	x	x	x	x	x	x	x	
Device deficiency assessment - Weekly		x	x	x	x	x	x	x	x	x	x	x	x	x	x	x	x	x	x	
Usability  - Weekly		x	x	x	x	x	x	x	x	x	x	x	x	x	x	x	x	x	x	
Reliability 																			monitored continuously during this period	
Adverse Events																			collected continuously during this period	
Concomitant Medications 																			collected continuously during this period	
Reason for withdrawal - Weekly		x	x	x	x	x	x	x	x	x	x	x	x	x	x	x	x	x	x	
Review of HCP support & interactions  - Monthly		x	x	x	x	x	x	x	x	x	x	x	x	x	x	x	x	x	x	

Month(s)	19	20	21	22	23	24	25	26	27	28	29	30							Withdrawal
Vital signs – Weekly	x	x	x	x	x	x	x	x	x	x	x	x	x	x	x	x	x	x	x
RO water/dialysate quality  - Monthly	x	x	x	x	x	x	x	x	x	x	x	x	x	x	x	x	x	x	x
Device deficiency assessment - Weekly	x	x	x	x	x	x	x	x	x	x	x	x	x	x	x	x	x	x	x
Usability  - Weekly	x	x	x	x	x	x	x	x	x	x	x	x	x	x	x	x	x	x	x
Reliability 																			monitored continuously during this period
Adverse Events																			collected continuously during this period
Concomitant Medications 																			collected continuously during this period
Reason for withdrawal - Weekly	x	x	x	x	x	x	x	x	x	x	x	x	x	x	x	x	x	x	x
Review of HCP support & interactions  - Monthly	x	x	x	x	x	x	x	x	x	x	x	x	x	x	x	x	x	x	x

 Water/dialysate samples will be collected and tested monthly Participants queried: required assistance with any aspect of treatment over the prior 7 days and if so, with which of the following tasks: machine set up, clearing of alarms, machine take down, fistula/needling or catheter connection Ability to deliver prescribed treatments Concomitant medication collection will be limited to the following: erythropoiesis-stimulating agents (ESAs), intravenous iron, phosphate binders, calcimimetics, and anti-hypertensive medications (ACE inhibitors, ARBs, beta blockers, calcium channel blockers, central alpha agonists, vasodilators [specifically, hydralazine and minoxidil]). Collected monthly: HCP support and interactions are intended to be available to participants as required by the study, but not to provide additional training, support, or oversight of the dialysis procedure. Any contact outside study-driven procedures will be documented for purpose of understanding need for additional health care support.

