#### 9.1.1 Adverse Event

Any Adverse Event is defined as any untoward medical occurrence, unintended disease or injury, or untoward clinical signs (including abnormal laboratory findings) in participants, users or other persons, whether or not related to the investigational medical device.

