### 9.2 Adverse Event Relationship

All adverse events will be assigned an initial attribution according to the Investigator's believed primary cause. Events will be categorized by relationship to the investigational device, index procedure, concomitant medications, pre-existing condition, intercurrent condition, intercurrent intervention, or other.

*Investigational Device Related Adverse Event:* An adverse event, which in the judgment of the Investigator, results from use of the Quanta SC+ DDS.

*Non-Investigational Device:* It is reasonable to believe that the event is associated with an accessory device used during the study procedure and is not specific to the investigational device use

*Procedure Related Adverse Event:* An adverse event which, in the judgment of the Investigator, results as a consequence of dialysis independent of the use of the Quanta SC+ DDS.

*Medication-Related Adverse Event:* an adverse event is considered to be medication related when, in the judgment of the Investigator, it is reasonable to believe that the event is associated with any medications used.

*Pre-Existing Condition-Related Adverse Event:* an adverse event is considered to be related to a pre-existing condition when, in the judgment of the Investigator, it is reasonable to believe that the event is associated with the participant's pre-existing condition and is not specific to the investigational device or index procedure or medication to address heart failure. Pre-existing conditions that are aggravated or become more severe during or after the index procedure should be evaluated on a case-by-case basis to determine if the event may be more appropriately classified as device- or index procedure-related.

*Intercurrent Condition:* It is reasonable to believe that the event is directly associated with an intercurrent condition/co-morbidity.

*Intercurrent Intervention:* It is reasonable to believe that the event is directly associated with an intercurrent intervention which was performed for reasons other than to address a device- or index procedure-related complication.

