### **9.4 Adverse Events Recording and Reporting**

#### **9.4.1 All Adverse Events**

All Adverse Events and Device Related Adverse Events will be recorded as part of this study beginning from first treatment with the Quanta SC+ DDS. Participants will be asked at each encounter an open-ended question such as, "How have you been feeling since your last visit?" and any events meeting an adverse event definition will be recorded. Clinic progress notes and other medical records will also be reviewed to determine if adverse events have occurred.

All adverse events (i.e., serious or non-serious, anticipated or unanticipated) must be recorded on the Adverse Event CRF by the Investigator or designee, for events of hypotension a specific eCRF should be used to ensure all details regarding event are recorded. All device deficiencies should be recorded on the device observations eCRF. The record must include the start date of the adverse event, treatment, resolution, and assessment of both the seriousness and the relationship to the investigational device.

The following criteria must also be adhered to by the Investigator:

- Completion of a separate Adverse Event form or log entries to document each event
- Completion of separate device observation form or log entries for each device observation or deficiency
- Electronic signature of forms or log entries
- On request of the sponsor, provision of any additional information related to the safety reporting of a particular event

All adverse events will be reported by the Sponsor or designee to the applicable regulatory authority at least annually or as required and to IRBs as instructed by the applicable IRB.

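### In the extended phase, participants are told to report device-related events, which is narrower than the Section 9 all-AE reporting that Section 16 applies to the same phase

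*Protocol*

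**What the plan says.** Protocol Section 16 allows participants who complete the main study to stay on the device at home under a new consent, for at most 30 months or until FDA clearance. On safety it says three things:

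- After study completion "the subjects may remain enrolled in the study and undergo safety reporting as defined in" Section 9.
- Visits that collect endpoint data are no longer scheduled.
- "Subjects will be instructed to report any device-related medical events or deficiencies throughout the extended treatment phase".

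The Section 16 table has an Adverse Events row marked "collected continuously during this period", with no limit to device-related events, and the row is repeated for months 19 to 30.

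Section 9 is broad. Section 9.1.1 defines an AE as an untoward occurrence "whether or not related to the investigational medical device". Section 9.4.1 says "All Adverse Events and Device Related Adverse Events will be recorded as part of this study beginning from first treatment with the Quanta SC+ DDS". Section 9.2 says "All adverse events will be assigned an initial attribution according to the Investigator's believed primary cause".

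SAP 12.2 repeats the device-related instruction, gives 18 months as the limit, and does not mention Section 9.

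**The concern.** Two reporting rules apply to one phase. Section 9 asks for every AE and leaves cause to the investigator. The sentence addressed to participants asks for device-related events and deficiencies. A participant who follows that sentence has to decide what is device-related before deciding what to report. Section 9.2 makes this a fine distinction, because it separates events due to the device from events due to dialysis in general. Patients and care partners are not well placed to draw that line.

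Two things depend on what is reported. The first is oversight: under Section 14.7 the safety and clinical events committee (SCEC) reviews serious adverse events (SAEs) reported in this phase, and the sponsor monitors the AEs reported. The second is the summary of extended-phase data promised in Section 16 and SAP 12.2. An access infection or a hypotensive episode that the patient puts down to dialysis or illness is the kind of event that could be held back until someone asks.

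**Working it through.** The documents give no figure to reproduce on this point, so the main check sets the passages side by side.

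**1. Scope of AE reporting, by place**

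| Place | Whom it addresses | Scope |
|---|---|---|
| Section 8.1 (main study) | Participants | AEs recorded continually between visits, no device limit |
| Section 9.1.1 | Definition | Any untoward occurrence, related or not |
| Section 9.4.1 | Site | All AEs, from first treatment on the device |
| Section 16, reference to Section 9 | Extended phase | As Section 9 |
| Section 16 table | Extended phase | AEs, continuous, no device limit |
| Section 14.7 | SCEC, extended phase | Reported SAEs, no device limit |
| Section 16 instruction | Participants, extended phase | Device-related events or deficiencies |
| SAP 12.2 | Participants, extended phase | Device-related events or deficiencies |

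Only the last two rows are narrow. Section 8.1 shows that the participant instruction shrinks between the main study and the extension. Everything else in Section 16 shows that the scope of collection is not meant to shrink.

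**2. Who judges relatedness**

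Section 9.2 gives the initial attribution to the investigator. In the extension, Section 14.7 has the SCEC adjudicate SAEs. Neither place gives participants a role, but the instruction requires one of them.

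**3. Routes that do not depend on the participant's view of cause**

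- Section 9.4.1: "Participants will be asked at each encounter an open-ended question such as" how they have been feeling.
- Section 9.4.1: "Clinic progress notes and other medical records will also be reviewed to determine if adverse events have occurred".
- The device deficiency assessment, weekly in the Section 16 table. Section 8.3 defines it as covering unexpected signs or symptoms as well as device complaints.
- Section 9.4.2: SAEs go to the sponsor within 24 hours of the investigator learning of them, however they came to light.

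These are real safeguards. There are two gaps. The questions are tied to encounters, and Section 16 does not say which extended-phase contact carries the open question. The Section 16 table also omits the treatment flowsheet, on which home participants record symptoms during dialysis (Section 8.4.2), and Section 16 does not mention the mid-week home visit, which includes an AE assessment in the main study (Section 8.3).

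**4. Exposure, for scale only**

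Treatments per participant = months × 365.25/12/7 × sessions per week. In the extension the treating nephrologist sets the prescription, so 3 to 5 sessions per week is an assumption. The main home phase has 4 × 8 = 32 treatments. The planning rate of 0.03 per treatment (Section 10.2.2) is for pre-specified AEs, not all AEs.

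| Limit | Weeks | Sessions/week | Treatments | Multiple of 32 | Pre-specified AEs at 0.03 |
|---|---|---|---|---|---|
| 30 months (protocol) | 130.4 | 3 / 4 / 5 | 391 / 522 / 652 | 12.2 / 16.3 / 20.4 | 11.7 / 15.7 / 19.6 |
| 18 months (SAP) | 78.3 | 3 / 4 / 5 | 235 / 313 / 391 | 7.3 / 9.8 / 12.2 | 7.0 / 9.4 / 11.7 |

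These are maxima for one participant who stays to the limit. They show that the extension can hold far more home exposure per person than the main study. They do not show how many events would be missed.

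**5. What cannot be computed**

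If r is the true rate per treatment, T the number of treatments and m the share missed, then m × r × T events are lost and the apparent rate is r × (1 − m). The documents give no value for m, none for the all-AE rate, and no number of participants expected to enter or stay in the extension.

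**The case against.** The strongest reply is that the instruction does not say that participants report device-related events and nothing else. It follows the reference to Section 9 by two sentences and can be read as an extra duty on top of it. The new consent form, which may contain the full instruction, is not among the documents. The site still asks the open question and reviews records, the weekly assessment still asks about symptoms, and the site investigator is the treating nephrologist and must record all AEs. The extension data are also excluded from the primary and secondary analyses.

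Most of this stands, and it limits how far the point can go. A reader might infer that harms not blamed on the device go uncounted for 30 months. The documents do not support that: the routes above can capture such events, and 30 months is a ceiling that FDA clearance can shorten. A reader might also infer that device-related events which patients fail to recognise would never reach the SCEC. That does not follow either. SAEs reach it through the investigator, and non-serious AEs are outside its extended-phase review by design. Nor is there a planned comparison in which a low extension rate would look better than the main home-phase rate.

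What the reply does not remove is the mismatch. An additional duty would not need to be narrower than the rule it adds to. SAP 12.2 states the narrow version without the Section 9 reference, so read alone it describes device-related reporting. The safeguards confirm that all AEs are meant to be collected, and that is the reason to align the instruction.

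**Conclusion.** The contradiction is real and sits within one paragraph of Section 16, repeated in SAP 12.2. The consequence is a risk of under-reporting, between contacts, of events that participants do not attribute to the device. It bears on continuing safety oversight and on the descriptive extension summary. It does not touch the success criteria or any primary or secondary endpoint.

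The size cannot be estimated. Any count of lost events would need an assumed missed share, an assumed number of participants continuing and an assumed session frequency, and the documents supply none of these. The conclusion rests on two readings: that participants take the instruction as written, and that no fuller instruction in the new consent form overrides it. The second cannot be checked from the documents.

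The change is worth making because it is cheap and brings the instruction into line with the plan's own rule.

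**What to change.** Reconcile the passages as follows.

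- In Section 16 and SAP 12.2, instruct participants to report any adverse event and any device deficiency, whether or not they think it is device-related. Carry the same wording into the participant materials for the extension.
- In Section 16, state that the Section 9.4.1 open question is asked at the weekly assessment already in the table.
- Leave relatedness with the investigator and, for SAEs, with the SCEC.
- While SAP 12.2 is open, align its 18-month limit with the protocol's 30 months. The SAP was prepared from protocol Rev. 1.8, before version 1.9 lengthened the phase.

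The cost is a short text change in each document and somewhat more AE entries for sites. No new visits are needed, and no endpoint analysis changes.

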## 17 DOCUMENT REVISION HISTORY

Issue	Date	Changes
v1	01 FEB 2021	Initial protocol
v1.1	26 May 2021	Added transition phase between clinic and home phases Added requirement for insurance coverage to inclusion criteria Added requirement for dialysis visits on specific days of the week Updated number of sites including addition of Canada Updated primary and secondary endpoints to include comparison of all AEs in-home and clinic Updated schedule of assessments and visits schedule for consistency Updated Bibliography to include references related to the additional Patient report outcomes

V1.2	14 July 2021	Removed foreign clinical site, Health Canada (HC) Updated total number of sites from 10-15 to 8-15 for US Updated Section 8.3.5 to allow for clinical sites to provide supplies per local protocols/requirements Editorial correction in Synopsis inclusion criteria (re. care partner statement) to be consistent with Section 7.2.1. Updated section 8.3.2 to standardize method of heparin delivery
V1.3	10 August 2021	Updated section 8.3.2 to add back heparin administration requirement for patients with AVF/AVG Updated section 8.3.5 to add back heparin and syringe supplies
V1.4	30 November 2021	Updated Section 2 to include pregnancy test, updated footnotes (4, 6, 9, 15) in Section 2 for clarification, Updated exclusion criteria to clarify blood work duration during enrollment, clarification updates to section 8.3.5 and 8.4.1, updated visits schedule for consistency with section 2, Clarification update to section 8.3.1, Updated Section 7.4 to increase threshold for withdrawal criteria, minor editorial corrections.
V1.5	17 January 2021	Added study name (HOME RUN), clarification updates to Inclusion/Exclusion criteria, updated albumin target range, removed specific requirement for pregnancy test from the schedule of assessment, multiple editorial corrections in visits schedule to align with Section 2, updated Section 8.3 for managing clinical utility data upload on eCRF.
V1.6	14 February 2022	Reverted changes regarding pregnancy exclusion criteria.
V1.7	14 March 2022	Updated statistical considerations for this protocol based on CMS feedback – specifically updated the Intent-to-Treat analysis population in Section 10.3.1 to the Full Analysis Set (as well as replaced ITT with FAS throughout the document). Additionally, we updated Section 10.6 to describe the analysis approach for the patient reported outcome secondary endpoints, as advised by CMS.
V1.8	13 July 2022	Updated section 1, participants- increased to 50 participants, included peritoneal dialysis patients, increased to 25% of participants to be recruited from a single site; updated section 1, inclusion criteria- included peritoneal dialysis patients; updated section 2- removed participant portal from schedule of assessments; updated section 6.2.2, deleted (UF) 10% of expected next fluid removal per hour, based on the UF prescription; updated section 6.4, participant population and numbers- increased to 50 participants, included peritoneal dialysis patients, increased to 25% of participants to be recruited from a single site; updated section 7.2.1 Inclusion criteria-, included peritoneal dialysis; updated section 8.1, visit schedule, clinic period- removed digi health training and replaced with Training on ipad and associated apps; section 8.3.4, deleted software portal section and added treatment flowsheet section; updated section 8.3.6, Dialysis Prescription- included Dialysate Conductivity (13.7 – 14.1 mS/cm) and Bicarbonate (35 mmol/L); and updated section 10.2.2, primary safety endpoint- increased total number of patients to 50; added section 16- Extended Treatment Phase; Section 16, document revision history, became section 17;

V1.9	15 February 2024	Updated protocol synopsis- U.S. Agent (sponsor) with U.S. sponsor address; section 14.7- specified that all AEs would be reviewed and device related AEs adjudicated by the SCEC during the primary study and SAEs reported during the extended treatment phase will be reviewed and adjudicated by the SCEC, specified that the SCEC would not be blinded as to whether an SAE occurred in the home or clinic during the extended treatment phase; section 16- the time period for the extended treatment phase was increased from 18 to 30 months and the additional months were added to the schedule of assessments for the extended treatment phase; device deficiency and usability assessments were added to include months 12-30.
------	------------------	-------------------------------------------------------------------------------------------------------------------------------------------------------------------------------------------------------------------------------------------------------------------------------------------------------------------------------------------------------------------------------------------------------------------------------------------------------------------------------------------------------------------------------------------------------------------------------------------------------------------------------------------------------------------------------------------------------------------------------------------

## APPENDIX: PROCEDURE FOR DEVICE- OR USER-RELATED ERRORS

From the beginning of the baseline period until study completion, the HF specialist will review each device error event and determine whether the event is likely to be use-related. As needed, the HF specialist will consult a Quanta systems specialist or the study site staff for input when determining whether an event is use-related or not. It is expected that some device error events might be induced by the user—for example, an alert that results from a user not opening a clamp at the appropriate time—whereas other device error events might be unrelated to user-device interactions. Device error events might be related to the SC+ system, software, hardware, or consumables, and could be encountered by study participants (e.g., patients, caregivers) as well as nurses participating in the trial. In the balance of this section, the term “study participant” is used to refer to any of the above individuals who might encounter a device error event during SC+ system use during the IDE clinical trial.

For all device error events that are definitely or likely use-related, the HF specialist will then reference a comprehensive list of critical tasks, identified based on the use-related risk analysis, to determine whether the device error event is related to a critical task or not. The list of critical tasks will be maintained in the study manual of operations and will be updated as needed to reflect any initially unanticipated critical tasks.

**For each device error event related to a critical task**, the following steps will be taken:

1. The HF specialist will determine what additional information is needed from the study participant to be able to analyse the root cause(s) of the error event
2. The HF specialist will engage the site coordinator or delegate to collect any additional information from the study participant, including subjective feedback regarding system use when the error event occurred and additional information regarding what might have led to the error; notably:
  - to supplement the training provided before the trial, the HF specialist will assist the site coordinator and/or delegate as needed to ensure they ask appropriate follow-up questions to facilitate unbiased and comprehensive root cause analysis
  - the HF specialist will not be in direct contact with the study participants at any time
  - the HF specialist will work closely with the site staff to ensure any HF work is performed without interfering with the primary objective of the IDE clinical trial
3. The HF specialist will review and analyse the data collected, including the event log information and subjective feedback collected during follow-up activities, to identify the root cause(s) of any use-related errors associated with critical tasks. The root cause analysis will aim to identify what, including any aspect of the SC+ user interface, home use environment, or other factor(s), contributed to the error.
4. The HF specialist will document the identified root causes in a format that will be determined by the CEC.
5. The CEC and other Quanta representatives, as appropriate, will be responsible for determining if any further risk control measures will need to be implemented.

Device error events that are deemed non-critical per the use-related risk analysis (i.e., errors related to use steps not associated with a potential for serious harm) are out of scope of the IDE clinical trial’s HF activities, in line with FDA’s HFE guidance for medical devices.

The following event framework is for use in approaching and categorising potential events that would require investigation by the Safety Team. It is derived from definitions defined in part by standards and in part by the Sponsor based on previous assessments, submissions and business definitions.

Level 1: Protective System Performance
 
Did a device failure of its constructional or functional safety compromise a risk control measure of the Hazard Analysis?
		
If Yes, investigate immediately with Sponsor.
 
If No, move to Level 2.

Level 2: Essential Performance
 
In accordance with IEC 60601-2-16, did the device fail to meet the tolerances specified by the Sponsor under normal conditions:
 
 
• Blood flow rate
 
• Dialysis fluid flow rate
 
• Net fluid removal
 
• Dialysis time
 
• Dialysis fluid composition
 
• Dialysis fluid temperature
 
		
If Yes, investigate immediately with Sponsor.
 
If No, move to Level 3.


Level 3: Usability
 
Did a Use Error event occur in which the user performed a task incorrectly (i.e., not in accordance with the intended manner of use) or did not complete a necessary task?
 
If Yes, move to Level 3a.
 
Or
 
Did a Close Call event occur in which the user performed or nearly performed a task incorrectly (i.e., not in accordance with the intended manner of use), but then resolved the issue prior to any harm being done without assistance.
 
Or
 
Did a Use Difficulty event occur in which the user struggled to some extent while
	
Level 3a: Critical Use Error
 
Was the use error for a task required for safe and effective use of the device, or a task with a harm severity classification for the use error that is:
 
Catastrophic:
 
Could result in death, or serious health impacts to multiple people, or major breach of regulation.
 
Critical:
 
Could result in life-threatening injury that requires specialist medical intervention and/or causes long term or permanent disability.
	
If Yes, investigate immediately with Sponsor.
 
If No, move to Level 3b.

completing a task (e.g., confusion, taking longer than expected, difficulty manipulating a device's components), but eventually completed the task successfully without assistance.
 
If Yes to Close Call or Use Difficulty, this should be investigated further with the Sponsor but no harm is associated with the event.
		
	
Level 3b: Non-Critical Use Error
 
Was the use error for a task with a harm severity classification for the use error that is:
 
 Serious:
 
 Could result in injury that requires general medical intervention and/or causes short-term disability.
 
 Minor:
 
 Could result in impaired device performance, or an injury that does not require trained medical intervention.
 
 Negligible:
 
 Could result in inconvenience or minor temporary discomfort only.
	
If Yes, this should be investigated further with the Sponsor, but no harm is associated with the event.
 
If No, move to Level 4.


Level 4: Reliability
 
Where a treatment or treatment setup initially fails, but can be restarted, a treatment is effectively delivered so is not discounted for purposes of the IDE. Reliability events are
		
If Yes, this should be investigated further with the Sponsor, but no harm is associated with the event.
 
If No, move to Level 5.

categorised based on the following:
 
Did the treatment duration increase <math>\geq 2.5\%</math> over the planned treatment time due to unplanned interruptions in treatment within the influence of the device?
 
Or
 
Was treatment or setup prevented by machine action such as a self-test failure or an alarm?
 
(Nb. This is not a failure of the Protective System or Essential Performance.)
 
Or
 
Did the user identify a device defect prior to use?
		

Level 5: To Be Determined
 
This is the end of the event framework. If an event does not fall into any of the above levels, then it should immediately be investigated further with the Sponsor to ensure no harm is associated with the event.

